#### Aim 1C. Demonstrate feasibility of study procedures (primary outcomes: recruitment and retention).

**H1:** Recruitment rate will be ≥ 40% at each site.

**H2:** Retention rate will be  $\geq 75\%$  at each site and in each arm.

Feasibility will be assessed using both recruitment and retention rate. Recruitment rate is the proportion of individuals who passed the online eligibility screen (denominator) who enroll in the study at the Month -1 inperson intake session (numerator). Retention rate is the proportion of participants who were randomized to treatment arm (denominator) who complete the primary clinical outcomes at Month 3 (numerator). Both recruitment and retention rates will be calculated for each site. A site will be considered to demonstrate adequate feasibility of study procedures if the recruitment rate is  $\geq 40\%$  and the retention rate is  $\geq 75\%$ . An arm will be considered to demonstrate adequate study feasibility if the retention rate is ≥ 75%.

#### Sample Size Justification and Power for Aim 1

The n = 144 will allow each site to have 2 treatment groups within each MBCT treatment arm and maintain 1:1:1 treatment arm assignment; for example, at the NYULH site, the total n = 48: MBCT-T (2 treatment groups, n = 16 per site), MBCT-V (2 treatment groups, n = 16 per site) and EUC (n = 16 per site).

Power calculations were informed by preliminary data (Ms, SDs). For Aim 1A, 100% of sessions met the benchmark in preliminary testing; within a 95% CI, we will have power above .99 to detect a mean fidelity score at or above the benchmark. For Aim 1B, 87% of participants met benchmarks for both feasibility and acceptability in preliminary testing; within a 95% CI we will have power above .89 to detect mean feasibility and acceptability score at or above the benchmarks. For Aim 1C hypothesis 1, we will be able to estimate a recruitment rate of 40% to within a 95% confidence interval of +/- 5% for the study overall (enrolled n = 144) and +/- 9% for each site (enrolled n = 48). For Aim 1C hypothesis 2, we will be able to estimate a retention rate of 70% to within a 95% confidence interval of +/- 7% for the study overall and (n = 144) +/- 13% for each site (n = 48).

#### Aim 2. Use decision rules to determine design for future fully-powered Phase III trial.

#### **Decision Rules**

Decision rules will be assessed using data pooled across sites to reduce multiple comparisons and discrepant findings across sites. However, we anticipate that certain sites will have strengths and weaknesses related to feasibility and acceptability outcomes. We hope to use ongoing monitoring to identify weaknesses during the study and implement procedures to improve sites falling behind on outcome parameters. We also will evaluate feasibility information at each site to determine whether to keep/remove the site for a future trial, or whether the site (and other potential sites with similar characteristics) requires different resources to be successful.

Decisions rules are based on three levels where we will consider benchmarks, clinically important differences (CIDs) between groups, and statistical significance.

Benchmarks (MBCT-T and MBCT-V): MBCT-T and MBCT-V will need to meet minimum benchmarks for primary outcomes (fidelity, feasibility, and acceptability) across treatment arm and site. Primary outcomes:

Version date: 3/8/2022

Fidelity (MBCT-TACS scores  $\geq$  2.5), Feasibility of treatment (75% Session Attendance), Acceptability of treatment (Client Satisfaction Questionnaire-8 (CSQ-8) score > 24), Feasibility of study procedures (recruitment rate will be  $\geq$  40%; retention rate will be  $\geq$  75%).

If one or more of these thresholds is not met for MBCT-T or MBCT-V for all sites, we will examine secondary outcomes to help determine the cause of suboptimal performance, make changes to the treatment arm and/or site, and/or conduct an additional pilot to rectify performance. If thresholds are not met for treatment arm, we will not move forward with a future trial with either MBCT-T or MBCT-V. If thresholds are not met for site, we will ascertain whether the identified barrier to fidelity, feasibility, and/or acceptability is modifiable. If barrier is deemed to be unchangeable, we will consider dropping the site in fully-powered trial.

**Benchmarks** (EUC): EUC will need to meet minimum thresholds for feasibility and acceptability indicated above. If either or both of these domains are not met, we will use secondary outcomes to improve feasibility and/or acceptability in future pilot testing prior to moving forward with the fully-powered Phase III clinical trial. If both acceptability and feasibility benchmarks are met for EUC, we will move forward with EUC in a future Phase III trial.

## Clinically Important Differences (CIDs) and statistical significance

If minimum benchmarks (see above) for all arms are met, we will move forward with **both MBCT-T** and **MBCT-V** vs. **EUC** in a fully-powered Phase III clinical trial **so long as neither version of MBCT is superior to the other based on the following analyses:** 

- 1) **MBCT-T/V Treatment fidelity**: MBCT-TACS is at least ≥0.2 points higher in the superior compared to the inferior arm, and this difference is statistically significant.
- 2) **MBCT-T/V Treatment feasibility** is at least 15% higher in the superior arm compared to the inferior arm, and this difference is statistically significant.
- 3) **MBCT-T/V Treatment acceptability** is at least 5 points higher in the superior arm compared to the inferior arm, and this difference is statistically significant.
- 4) MBCT-T/V Clinical utility: 50% responder rate for the HDI (10-point change from M0-M3) and the QIDS-SR (5-point change from M0-M3). No significance testing between MBCT-T and MBCT-V will be conducted for this outcome.

If one of the above criteria is met (i.e., one treatment meets threshold for being superior to the other), we will select this treatment to move forward with further testing in a fully-powered Phase III trial.

If we observe mixed results (e.g., MBCT-T is superior on feasibility but MBCT-V is superior on clinical utility) we will utilize results from secondary outcomes to further explore differences between the MBCT-T and MBCT-V treatment arms to inform the selection of treatment arms for the Phase III trial.

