This material is the property of the NYU School of Medicine and NYU Langone Health. Do not disclose or use except as authorized in writing by the study sponsor

Version date: 3/8/2022

Time Frame: The measure is administered in the daily diary from Screening through Month 3 on

days during which a headache was recorded.

Brief Description: On each day when a participant reports they had a headache, participants will be

asked to rate their pain on a scale from 0-10, with 0 indicating no pain, 1-3 indicating

mild pain, 4-6 indicating moderate pain, and 7-10 indicating severe pain.

Name: Demographics

Type: Other Time Frame: M-1

Brief Description: Demographics will include age, sex, income, education, race, ethnicity, marital status,

family structure, and occupation.

Name: Client Satisfaction Questionnaire – 8 (CSQ-8)

Type: Primary

Time Frame: M2, M3, M6, M9

Brief Description: The CSQ-8 assesses treatment acceptability. The CSQ-8 is an 8-item self-report

measure designed to assess satisfaction with mental health services. Response options are coded on a 4-point scale and summed to produce a total score ranging from 8-32. The measure has consistently demonstrated excellent reliability and validity, and is commonly used in behavioral treatment trials. For the purposes of this

study, we consider "acceptable" to be a CSQ-8 score > 24 at Month 2.

Name: Five Facet of Mindfulness Scale (Short Form; FFMQ-15)

Type: Secondary
Time Frame: M0 and M2

Brief Description: The FFMQ is a measure of treatment fidelity. The FFMQ measures pre-post trait

mindfulness and is assessed using 15 items that index the degree to which participants experience daily mindfulness, a central objective of the MBCT-T

treatment. Each item is rated on a 5-point scale from '1' = never or very rarely true to '5' = very often or always true. An example item is "When I take a shower or a bath, I stay alert to the sensations of water on my body." Scores range from 15-75, with

higher scores reflecting greater trait mindfulness.

Name: Headache Management Self-Efficacy Scale (HMSES)

Type: Secondary
Time Frame: M0 and M2

Brief Description: For the EUC group, we will assess self-efficacy for headache self-management skills

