#### Aim 1B. Demonstrate feasibility and acceptability of MBCT-T, MBCT-V, and EUC.

H1: MBCT-T, MBCT-V, and EUC will be feasible [Primary Outcome: 75% Session Attendance] and acceptable [Primary Outcome: Client Satisfaction Questionnaire-8 (CSQ-8) score > 24] at each site.

Feasibility is assessed using Treatment Session Adherence (n = 144), which will be summed to indicate the number of treatment sessions attended. Descriptive statistics (mean and standard deviation) will be calculated for Treatment Session Adherence across each treatment arm (MBCT-T, MBCT-V, EUC) and each site (NYULH, Montefiore, WFBH). A treatment arm will be considered feasible if on average participants attended 75% of sessions, across all sites. A site will be considered to demonstrate adequate feasibility if on average participants attended 75% of sessions across treatment arms at the site.

Version date: 3/8/2022

Acceptability is assessed using the CSQ-8 at a single time-point. Descriptive statistics (mean and standard deviation) will be calculated for the CSQ-8 across each treatment arm (MBCT-T, MBCT-V, EUC) and each site (NYULH, Montefiore, WFBH). Investigators will endeavor to obtain CSQ-8 scores from all participants; if participants drop out of the study prior to Month 2 and cannot be reached to complete this measure, a total score of 8 will be imputed for these missing data, indicating dissatisfaction with the treatment across all domains. A treatment arm will be considered acceptable if CSQ-8 scores are > 24, across all sites. A site will be considered to demonstrate adequate acceptability if on average participants report CSQ-8 scores > 24 across treatment arms at the site.

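### Imputed 8s, combined with the >24 precondition and the 32-point ceiling, let the CSQ-8 superiority rule turn on which MBCT arm lost people, and the quoted power of .91 is not the chance that the rule fires.

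*Combined protocol and SAP*

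**What the plan says.** - **Precondition.** The subsection on clinically important differences in Section 9.1 begins "If minimum benchmarks (see above) for all arms are met, we will move forward with" both MBCT versions against EUC, provided neither MBCT version is superior. All three arms, including EUC, must therefore pass first.
- **Benchmark.** The Decision Rules list "Acceptability of treatment (Client Satisfaction Questionnaire-8 (CSQ-8) score > 24". Aim 1B adds "A treatment arm will be considered acceptable if CSQ-8 scores are > 24, across all sites".
- **Rule 3 (acceptability).** One MBCT version is superior if its CSQ-8 result "is at least 5 points higher in the superior arm compared to the inferior arm, and this difference is statistically significant".
- **Scale.** In Section 7.2.1.5 the items are "summed to produce a total score ranging from 8-32", and acceptability is judged at Month 2.
- **Missing scores.** The opening of Section 9.1 replaces missing CSQ-8 values by the scale minimum, as a general rule. For people who leave before Month 2 and cannot be reached, Aim 1B says "a total score of 8 will be imputed for these missing data, indicating dissatisfaction with the treatment across all domains".
- **Analysis and power.** The Analyses subsection plans a mixed model of 96 participants with site as covariate and quotes power of .91 for a 5-point difference, from preliminary SDs and ICCs that it does not give. It does not mention the imputation, the precondition or the scale ceiling.

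**The concern.** Aim 2 exists to choose the Phase III arms by pre-specified rules. Rule 3 is meant to detect a difference in satisfaction between telephone and video delivery. Two features distort it. The precondition leaves the higher arm a band of only 3 points. The imputed 8s then act in opposite directions depending on which arm they fall in: they block the rule in one and help it in the other. A result labelled as acceptability may therefore reflect differential dropout, which the >24 benchmark and the retention benchmark already penalise. A reader of the power statement would also expect rule 3 to succeed about nine times in ten when the true difference is 5 points, which is not what .91 measures.

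**Working it through.** **Inputs.** 48 per MBCT arm (Section 5.6: 16 per arm at each of three sites); scale 8 to 32; benchmark above 24; margin 5; imputed value 8; two-sided alpha 0.05. Decision rules use data pooled across sites. I assume raw arm means and that the imputed scores enter the comparison.

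**1. The stated power.** No SD or ICC is given, so I solve for the spread that yields .91. With SD × √(design effect) = 7.42, the standard error is 7.42 × √(2/48) = 1.515, and 5/1.515 − 1.96 = 1.34, which gives power .91. For clusters of 8, assumed ICCs of 0 to 0.20 correspond to SDs of 7.4 to 4.8. The figure is attainable as power for significance.

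**2. Power is not the chance that the rule fires.** With that standard error, a difference of 1.96 × 1.515 = 2.97 is already significant, so the 5-point margin is the binding condition. If the true difference is exactly 5, a roughly symmetric estimate reaches 5 about half the time, before the precondition is applied.

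**3. Ceiling in the higher-scoring arm.** The lower arm needs a total of at least 24 × 48 + 1 = 1153, so the higher arm needs at least 1153 + 5 × 48 = 1393. With k scores set to 8, its maximum total is 32(48 − k) + 8k, a maximum mean of 32 − 0.5k. The completers must average (1393 − 8k)/(48 − k).

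| k missing, higher arm | Maximum total | Completer mean needed |
|---|---|---|
| 0 | 1536 | 29.02 |
| 2 | 1488 | 29.93 |
| 4 | 1440 | 30.93 |
| 5 | 1416 | 31.47 |
| 6 | 1392 | 32.02 (impossible) |

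At an assumed loss of 5%, 10% or 15%, the binomial chance of six or more missing out of 48 is 0.03, 0.35 or 0.75.

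**4. The same loss in the other arm.**
- Six missing in the lower arm, none in the higher: the lower completers need (1153 − 48)/42 = 26.31 and the higher arm 1393/48 = 29.02. A completer gap of 2.71 meets the margin. With an assumed completer SD of 3, the lower-arm variance is 0.125 × 0.875 × 18.31² + 0.875 × 9 = 44.5, the standard error is √((44.5 + 9)/48) = 1.06, and 5/1.06 = 4.7, so it is also significant in a simple comparison.
- Six missing in the higher arm, none in the lower: completers at 32 against 24.02 give 29.00 − 24.02 = 4.98. A completer gap of 7.98 fails.

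**5. Illustrative simulations.** Assumptions: completer scores rounded and capped at 32, SD 3, 48 per arm, simple t-test. The full rule means all of: both MBCT arms above 24, observed difference at least 5, and significance.

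| Latent completer means | Loss | Significance | Full rule |
|---|---|---|---|
| 30.5 vs 25 (29.91 vs 25.00 after the cap) | none | 1.00 | 0.44 |
| 30.5 vs 25 | 5% both arms | 0.985 | 0.11 |
| 31 vs 26 | 10% both arms | 0.80 | 0.03 |
| 31 vs 26 | 12.5% both arms | 0.71 | 0.01 |
| 31 vs 26.5 | 12.5%, lower arm only | 1.00 | 0.44 |
| 33 vs 25 (31.24 vs 24.99 after the cap) | none | 1.00 | 0.98 |

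Raising the assumed SD to 4 or 5 at the same latent means lowered the no-loss probabilities. The last row shows that the rule does work when the gap is well above 5 and nobody is missing.

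**6. The 15% in rule 2.** Starting from 75% attendance, percentage points require 75 + 15 = 90% in the higher arm. A relative reading requires 75 × 1.15 = 86.25%. The plan does not say which.

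**The case against.** The best defence is that a demanding margin between two acceptable arms is a legitimate pilot choice with a safe default: if no rule fires, both MBCT versions go forward. The imputation also guards against an arm looking good because its dissatisfied participants left, and the plan limits missingness by trying to obtain CSQ-8 scores from everyone. All of this stands, and it rules out several stronger readings that a reader might infer:

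- **That six missing scores anywhere disable rule 3.** Only those in the higher-scoring arm do.
- **That the plan accepts 12 of 48 missing CSQ-8 scores.** The retention benchmark counts completion of the HDI and QIDS, not the CSQ-8.
- **That attendance has the same defect.** It has no score imputation, and on the percentage-point reading the higher arm still has 90% to 100% and the lower 75% to 85%.
- **That the Phase III choice must fall on fidelity and the responder rule.** The default is to keep both arms.
- **That .91 is wrong, or that the margins should be smaller.** Step 1 shows that .91 is attainable, and the documents give no basis for other margins.

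The defence does not answer the asymmetry. A low imputed score is a reasonable penalty in a benchmark for one arm. In a comparison of two arms it mixes satisfaction with dropout.

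**Conclusion.** The concern holds in this limited form, at moderate severity. If the imputed 8s carry into the Aim 2 comparison, six missing scores in a higher-scoring arm of 48 make rule 3 arithmetically impossible, and the same number in the lower arm lets a completer gap of about 2.7 meet a 5-point margin. The probability that rule 3 fires is also well below the quoted power when the true gap is near the margin: about half at a true difference of exactly 5 before the precondition, and a few percent at most in the simulations with 10% loss in both arms.

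The result rests on 48 per arm, raw pooled means, and the general imputation rule of Section 9.1 applying to the mixed model, which the Analyses subsection does not confirm. A site-adjusted estimate could move the threshold slightly, and arms of 49 or 50 could tolerate six missing. The loss rates, completer SD and latent means are assumptions, and the simulations ignore clustering and the EUC part of the precondition.

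**What to change.** In the subsection on clinically important differences and in Analyses:

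1. Compute the rule 3 comparison on observed Month 2 CSQ-8 scores. Keep the imputed 8 for the >24 benchmark, and report the imputed comparison as a sensitivity analysis.
2. Beside the .91, report the joint probability of precondition, 5-point margin and significance over a range of true gaps and loss rates, with the SD and ICC used.
3. State whether the 15% in rule 2 is percentage points or relative.

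The cost is wording and one recalculation, with no new data. There are two limits. Observed scores leave out dropouts, so an arm whose dissatisfied participants left could look better; those participants still count in the benchmark and in retention, and the sensitivity analysis shows their effect. Also, the benchmark still constrains the lower arm. With eight missing there, its completers must average at least (1153 − 64)/40 = 27.2, so the higher arm would need 32.2 and rule 3 could not fire. The joint probability in item 2 should make this visible.

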#### **Analyses**

Mixed effects models will evaluate whether treatment fidelity, treatment feasibility, or treatment acceptability differ significantly between MBCT-T and MBCT-V. Alpha will be set at 0.05 for all analyses.

To evaluate differences in fidelity, a multi-level linear mixed effects model will evaluate differences between MBCT-T and MBCT-V on the MBCT-TACS (72 sessions nested in 6 treatment groups). Treatment site will be included as a covariate. Repeated measures will be taken into account using session-level random effects.

To evaluate differences in feasibility and acceptability, two separate multi-level linear mixed effects model will be used to evaluate differences between MBCT-T and MBCT-V on Treatment Session Adherence and the CSQ-8 (96 participants nested in 6 treatment groups). Treatment site will be included as a covariate. Clusters

Version date: 3/8/2022

by group membership will be taken into account using random effects. Power for Aim 2. Using SDs and ICCs derived from preliminary data, with an n = 96 sessions and n = 96 participants, we have at least a power of .90 to detect the clinically important differences (CIDs) pre-specified in the decision rules for treatment fidelity (MBCT-TACS CID = 0.2 points; power > .99), treatment feasibility (Treatment Session Adherence CID = 15%; power > .99) and treatment acceptability (CSQ-8 CID = 5 points; power = .91).

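### The clinical-utility rule in Aim 2 can select one MBCT version for Phase III, but it states only an absolute 50% responder rate and no between-arm difference

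*Combined protocol and SAP*

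**What the plan says.** Under *Decision Rules* (section 9.1, Aim 2), the plan works at three levels: minimum benchmarks, clinically important differences between groups, and statistical significance. Data are pooled across sites.

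Under *Clinically Important Differences (CIDs) and statistical significance*, the starting point is "If minimum benchmarks (see above) for all arms are met, we will move forward with" both MBCT versions against EUC, "so long as neither version of MBCT is superior to the other based on the following analyses". Four analyses follow.

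- Rules 1 to 3 (fidelity, feasibility, acceptability) each set a between-arm margin of 0.2 points, 15% and 5 points, and also require significance. Rule 3, for instance, needs acceptability "at least 5 points higher in the superior arm compared to the inferior arm, and this difference is statistically significant".
- Rule 4 (clinical utility) reads "50% responder rate for the HDI (10-point change from M0-M3) and the QIDS-SR (5-point change from M0-M3", and adds: "No significance testing between MBCT-T and MBCT-V will be conducted for this outcome".

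The consequence is then stated: "If one of the above criteria is met (i.e., one treatment meets threshold for being superior to the other), we will select this treatment". Conflicting results go to the secondary outcomes, with the example that "MBCT-T is superior on feasibility but MBCT-V is superior on clinical utility".

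The *Analyses* paragraph gives models for rules 1 to 3 only. The sentence "we have at least a power of .90 to detect the clinically important differences (CIDs) pre-specified in the decision rules" is followed by figures for fidelity, feasibility and acceptability, and none for clinical utility. *Description of Statistical Methods* counts a missing responder result as non-response.

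**The concern.** Rule 4 has the form of a benchmark but sits in the list that decides superiority. It is meant to operate there: the plan's own example has one version winning on clinical utility, and section 3 names clinical utility among the rules that determine the Phase III arms. Because one criterion is enough, rule 4 can select an arm by itself. Yet it does not say what follows if both arms reach 50%, if neither does, or if an arm reaches it on one scale only.

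The word joining the two scales suggests that both are needed. It leaves open whether each scale's arm-level rate must reach 50%, or whether 50% of participants must respond on both.

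At stake is the choice of Phase III arms. A delivery mode that is just as good could be dropped by chance, or a real difference in response could go unnoticed. Someone would also have to interpret the rule after seeing the data, although Aim 2 calls the rules pre-specified.

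**Working it through.** **Inputs from the plan.** Section 5.6 gives 16 per arm per site at 3 sites, so 48 per MBCT arm. Results are pooled over sites. Missing counts as non-response, so the denominator stays 48 and 50% means at least 24. The plan states no error rate or power for rule 4, so there is no figure of its own to reproduce.

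**Assumptions, not in the documents.** The true responder rate p is shown as a range. Participants are independent unless an ICC is given. Rule 4 is read as: one arm reaches 50% and the other does not.

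**Step 1. Identical arms, one scale.** Let q = P(Bin(48, p) ≥ 24). The chance that exactly one of two identical arms passes is 2q(1 − q).

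| p | q | 2q(1 − q) |
|---|---|---|
| 30% | .003 | .006 |
| 35% | .023 | .045 |
| 40% | .103 | .19 |
| 45% | .290 | .41 |
| 50% | .557 | .49 |
| 55% | .800 | .32 |
| 60% | .940 | .11 |
| 65% | .989 | .022 |
| 70% | .999 | .002 |

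A single participant can decide it: 24/48 = 50.0% passes and 23/48 = 47.9% does not.

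**Step 2. Clustering.** Take each arm as 6 groups of 8 (2 groups per arm per site in section 5.6, groups of 8 in section 7.2.1.3.1) with beta-binomial counts. An assumed ICC of .05 to .1 gives .50 at 50%, .24 to .28 at 40% and .17 to .21 at 60%.

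**Step 3. A real difference.** With true rates of 70% and 90%, P(both pass) = .9989 × 1.0000 = .999. Under this reading the 20-point difference registers almost never.

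**Step 4. How the scales combine.** Identical arms, the same true rate on both scales, and an assumed latent correlation of .5 between them:

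| Rate on each scale | Each arm-level rate must reach 50% | Half of participants must respond on both |
|---|---|---|
| 50% | .46 | .025 (joint rate 33%) |
| 60% | .20 | .37 (joint rate 44%) |
| 70% | .004 | .29 (joint rate 56%) |

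The open choice can therefore move the chance of a split by a factor of ten or more, in either direction.

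**Step 5. Other readings of rule 4.** At p = 50% on one scale, if the higher rate simply wins, an arm is named unless they tie: 1 − .081 = .92. If rule 4 is only a per-arm benchmark, it names no superior arm at all.

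**Step 6. A between-arm margin.** Exact enumeration over 48 against 48, either direction, before any 50% condition. Margins of 10, 15 and 20 points need differences of 5, 8 and 10 participants.

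| Margin | Identical arms, p from 30% to 70% | Identical at 50%, ICC .1 | True 50% v 70%: better arm selected |
|---|---|---|---|
| 10 points | .32 to .36 | .48 | .86 |
| 15 points | .09 to .13 | .24 | .67 |
| 20 points | .03 to .05 | .14 | .51 |

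The 95% half-width for the difference near 50% is 1.96 × √(2 × .25/48 × (1 + 7 × ICC)) = .200, .232 and .261 for ICC 0, .05 and .1.

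**The case against.** **Leaving out the test is deliberate.** That stands: the plan says so, and with 48 per arm a test would have modest power. The gap is that no between-arm difference takes its place.

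**The mixed-results clause deals with doubtful cases.** It deals with criteria that point to different arms. When only rule 4 is met nothing conflicts, and the selection sentence applies.

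**The scales are combined, because the text joins them.** This stands in part. A reader might infer that the plan has no rule at all for combining the HDI and QIDS-SR. That goes too far, since the wording points to both being needed. What is missing is whether that means arm level or participant level.

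**The chance split rests on an assumed reading and an unknown rate.** This stands, and it limits the conclusion. A reader might infer that the plan will usually separate equal arms by chance, or that it prescribes selection at 24/48 against 23/48. The documents support neither. They do not state that reading, and for one scale with independent participants the split is about .05 or less at 35% and below or 65% and above.

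**A pilot may use judgement.** It may, but these rules are offered as pre-specified, and this one cannot be applied as written.

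**Conclusion.** The point holds in a conditional form. Rule 4 can select an arm for Phase III without stating what makes that arm better than the other, and nothing else in section 9.1 supplies the comparison. That much comes from the text alone.

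The size depends on the assumed reading, on 48 per arm and on the true responder rate. The chance that identical arms split is .49 at a true rate of 50%, and falls to .19 at 40% and .11 at 60%. With no expected rate in the documents, the risk is large only within about 10 points of 50%; clustering within groups widens that zone somewhat. Well above 50% the fault reverses, and a 20-point difference is missed. It should be fixed before the data are seen, but it does not touch rules 1 to 3.

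**What to change.** In the list under *Clinically Important Differences (CIDs) and statistical significance*:

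1. Keep the 50% responder rate as a condition on the arm to be selected.
2. Add a between-arm condition, for example a responder proportion at least 20 points higher than in the other MBCT arm, and report the difference with a 95% confidence interval. Expect a half-width of about 20 points near 50%, or 23 to 26 with an assumed ICC of .05 to .1.
3. State that the HDI and QIDS-SR must both be met, and whether at arm level or by the same participant. If at arm level, say whether the margin applies to each scale.

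The margin should be chosen with its chance of selecting between identical arms in view. Twenty points holds it to about .05 at any true rate (about .14 at 50% with an ICC of .1). Ten points would do worse than the reading examined here once the true rate is 60% or above.

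Moving the 50% rate into the minimum benchmarks is not a remedy. Benchmarks must be met by all arms before the comparison starts, and at a true rate of 50% at least one of two identical arms would miss it with probability 1 − .557² = .69.

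The cost is wording only, with no extra participants or data. The downside is sensitivity: at true rates of 50% against 70%, a 20-point margin selects the better arm only about half the time. A miss is mild, because both versions then go forward by default.
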